7.1.5.3 Survival follow-up phase

All patients will be followed for survival via a phone call (or during a clinic visit) every 12 weeks and up to one additional time per quarter if a survival update is required to meet safety or regulatory needs, until any of the following (whichever occurs first): death, withdrawal of consent, loss to follow-up, at least 18 months from when the last patient started treatment, or when 80% of patients have died or been lost to follow-up, or early study termination. Antineoplastic therapies or tumor directed surgical procedures initiated during the survival follow-up period must be recorded on the Antineoplastic Therapy since Discontinuation of Study Drug eCRF.

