10.5.3.1 Analysis set and grouping for the analyses

[figure not shown]
For all safety analyses, the Safety Set will be used. All listings and tables will be presented by treatment arm with patients classified according to treatment received.

The overall observation period will be divided into three mutually exclusive segments:

1. pre-treatment period: from day of patient's informed consent to the day before first dose of study drug
2. on-treatment period: from day of first dose of study drug to 30 days after last dose of study drug
3. post-treatment period: starting at day 31 after last dose of study drug.

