### **Cycle definition**

The study day for all assessments is calculated using the randomization date as Day 1.

The cycle number and day within cycle attributed to a visits or assessment will be derived according to the following rules:

- C1D1 (cycle 1 day 1) coincides with the start date of drug/treatment
- All pre-treatment assessments are displayed as **Cycle 0** with a negative day (e.g., **Day -1** for the day before the patient started treatment) or with day 1.
- Day 1 of a cycle corresponds to the day reported by investigator on the start of cycle log form.
- For all cycles but the last, the end date of a cycle is defined as the day before Day 1 of the following cycle as recorded on the cycle log form.
- The end date of the last cycle is when treatment administration is permanently discontinued at the latest of the following days:
  - Date of last administration
  - 28 days after the first day of the last cycle or day of patient's death if earlier when date of last administration is not known
- All post-cycles assessments are displayed as follow-up and with, by analogy, Day 1 representing the first day after the end of the last cycle.

The duration (in days) of a cycle is defined as the cycle end date – cycle start date + 1.

Cycle number and day within cycle are computed to be displayed in listings only.

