### **2.1.2.6 On-treatment assessment/event**

Safety summaries and selected summaries of deaths will summarize only on-treatment assessments/events. On-treatment assessment/event is defined as any assessment/event obtained in the time interval:

Date of first administration of study treatment through the date of last administration of study treatment + 30 days, i.e. including the lower and upper limits. (Note: However, the calculation of study treatment duration may use different rules as specified in [Section 3.3.1.1.](#))

Adverse events that begin or worsen after informed consent should be recorded in the Adverse Events CRF. Conditions that were already present at the time of informed consent should be recorded in the Medical History page of the patient's CRF.

If the last date of study treatment is missing, on-treatment assessments/events include any assessment/event recorded in the database and which occur after the start date of study treatment.

Data listings will include all assessments/events, flagging those which are not on-treatment assessments/events.

Note: The date of first administration of study treatment in the randomized treatment phase and the date of last administration of study treatment in the randomized treatment phase are defined in [sections 2.1.3.1](#) and [2.1.3.2](#), respectively.

For patients who crossed over to LEE011, the placebo group will include all events before the date of first administration of LEE011 and will not include the 30 days are described above. While the LEE011 crossed over group will include all events after the date of first administration of LEE011 and will include the 30 days.

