### **3.6.2 Deaths**

[figure not shown]
Summary of all deaths will be produced by treatment, system organ class and preferred term. All deaths will be listed for the FAS, on treatment deaths will be flagged.

[figure not shown]

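### The SAP's on-treatment fallback for a missing last dose date is not limited to patients still on drug, so late deaths and late related SAEs in a discontinued patient could be labelled on-treatment

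*SAP*

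**What the plan says.** SAP 2.1.2.6 sets the main window as "Date of first administration of study treatment through the date of last administration of study treatment + 30 days", with both limits included. It gives the label real work to do: "Safety summaries and selected summaries of deaths will summarize only on-treatment assessments/events". Listings show everything and flag what is not on-treatment. For a missing last date of study treatment the section switches to a fallback: "on-treatment assessments/events include any assessment/event recorded in the database and which occur after the start date of study treatment".

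Three other places bear on a patient who has stopped:

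- SAP 3.6 keeps data gathered more than 30 days after discontinuation out of the safety summary tables and flags them in listings. It makes no exception for a missing date.
- Protocol 10.5.3.1 divides observation into three exclusive segments. The last is the "post-treatment period: starting at day 31 after last dose of study drug".
- The SAP's Cycle definition, for treatment that has permanently ended, lets the last cycle close at "28 days after the first day of the last cycle or day of patient's death if earlier when date of last administration is not known". Later assessments are displayed as follow-up. The same section says that cycle number and day serve listings only.

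On deaths, SAP 3.6.2 asks for a summary of all deaths and adds: "All deaths will be listed for the FAS, on treatment deaths will be flagged".

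**The concern.** An open-ended window suits a patient who is still taking study drug at the cut-off, because no last dose exists yet. The fallback is not restricted to that patient. It applies equally to someone who stopped long ago and whose last dose date was never recorded. For that person the window never closes, and anything entered later counts as on-treatment.

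The label matters because the shortened report is largely a safety report. Adverse event and SAE summaries, the on-treatment death flag and the hepatic laboratory summary are all retained (SAP 3.6.1 to 3.6.3). A death from disease in survival follow-up, or a late SAE, could be presented as having happened on study drug.

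There is also a small wording mismatch. The fallback takes events after the start date, whereas the main rule and Protocol 10.5.3.1 include the day of first dose.

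**Working it through.** The plan states no figure for this point, so the check is a comparison of rules followed by date arithmetic on an assumed patient.

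**Step 1: one late event under each rule.** Take a discontinued patient with a fully missing last dose date and an event several months after stopping.

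| Source | Treatment of the event |
|---|---|
| SAP 2.1.2.6 fallback | On-treatment; not flagged as off-treatment in listings |
| SAP 3.6 | Outside the safety tables; flagged as late in listings |
| Protocol 10.5.3.1 | Post-treatment |
| SAP Cycle definition (listing label only) | Follow-up |

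The first row cannot be met together with the second or third. The fourth is a display label. It shows that the SAP anticipates this missing date and can put a limit on it.

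**Step 2: which dates trigger the fallback.** SAP 2.1.2.9 imputes the 15th when the day is missing and 1 July when day and month are missing. The fallback therefore matters mainly for dates that are wholly absent.

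**Step 3: what late data can exist.** Protocol Table 7-1 ends routine adverse event collection 30 days after last dose. Beyond that, Protocol 8.2.2 still takes in SAEs suspected to be related. Protocol 6.2.2 follows adverse events that led to discontinuation until they resolve or stabilise. Protocol 7.1.5.3 records survival every 12 weeks, with one possible end point being "at least 18 months from when the last patient started treatment" if no other condition comes first. The exposed items are chiefly late deaths and late related SAEs.

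**Step 4: size of the gap for an assumed patient.** The patient and dates are my assumptions: first dose 1 March 2015, Day 1 of the last cycle 21 June 2015, last dose date missing. For illustration, the window is closed with the Cycle definition's end date plus the standard 30 days.

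- Cycle end: 21 June + 28 days = 19 July 2015.
- Window closes: 19 July + 30 days = 18 August 2015, which is 28 + 30 = 58 days after last-cycle Day 1.
- Days outside the window = (days from last-cycle Day 1 to death) − 58.

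| Death, days after last-cycle Day 1 | Days outside the bounded window | Label under the fallback |
|---|---|---|
| 90 | 90 − 58 = 32 | on-treatment |
| 180 | 180 − 58 = 122 | on-treatment |
| 365 | 365 − 58 = 307 | on-treatment |
| 548 | 548 − 58 = 490 | on-treatment |

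On this comparison the two treatments of the missing date part company for any event more than 58 days after last-cycle Day 1.

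**The case against.** The best defence is that the damage is already contained. If SAP 3.6 is applied with the stopping date that Protocol 7.1.3 collects on the end-of-treatment eCRF, late events drop out of the safety tables. This stands for the tables. It does not reach the on-treatment death flag, the listing flags of 2.1.2.6 or the selected death summaries mentioned there, and it leaves the programmer to choose between two instructions.

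A second defence is that counting too much is a cautious choice when the end of exposure is unknown. That could be argued for a plan that chose it consistently, but SAP 3.6 states the opposite limit.

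A third is that the rule was meant for ongoing patients. The text does not say so. SAP 2.1.2.7 mentions, as an example, replacing a missing dose-record end date by the cut-off date. If that is done for ongoing patients, those left for the fallback are mainly the ones who stopped.

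It is also fair that the trigger is narrow, that little late data may exist, and that the placebo phase of a crossover patient is closed by the first LEE011 dose. These points limit the size of the problem but do not remove the conflict.

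A reader might go further than the documents allow in three ways:

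- That the Cycle definition is a rival on-treatment rule. It is not: it labels listings and imputes no last dose date.
- That a patient lost to follow-up is the natural example. Protocol 7.1.5.3 ends survival follow-up at that point, so such a patient would normally have no later data.
- That one mislabelled death would shift an arm's on-treatment death rate sharply. No output described in the documents is such a rate; SAP 3.6.2 summarises all deaths and flags the on-treatment ones in a listing.

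**Conclusion.** The concern holds as a minor correction. For a discontinued patient with a wholly missing last dose date, the fallback in SAP 2.1.2.6 contradicts SAP 3.6 and Protocol 10.5.3.1. Late deaths and late related SAEs would carry an on-treatment label in the death flag, in the listing flags and in any summaries restricted to on-treatment events.

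The practical effect depends on something the documents do not report: whether any of the 10 enrolled patients stopped treatment and lacks this date. If none does, the effect is zero. If one does, the error is in the timing label; no death is lost from the summary or the listing. The first-dose-day issue is a matter of wording, since the main rule already states that its limits are inclusive.

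**What to change.** In SAP 2.1.2.6:

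1. Restrict the open-ended rule to patients still on study treatment at the cut-off.
2. For discontinued patients with a missing last dose date, close the window 30 days after the treatment stop date on the end-of-treatment eCRF, with that date capped at death.
3. If the stop date is also missing, use the last-cycle end date from the Cycle definition (already capped at death) plus 30 days.
4. Write the lower limit as *on or after the start date*.

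In SAP 3.6, refer to the same derived date, so that tables, listing flags and the death flag agree.

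The cost is a few sentences and a short derivation from data already collected. The one drawback is that an event could be classed as post-treatment if dosing had continued unrecorded; it would still appear in the listings.

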### **2.1.2.7 Last contact date**

The last contact date will be derived for patients not known to be dead at the analysis cut-off using the last complete date among the following:

- All assessment dates (e.g. vital signs assessment, performance status/ [REDACTED]).

Note, only a true on study assessment date or patient contact date will be used. If there is a

visit date without evidence of any actual assessment performed that date will not be used. No dates post cut-off will be used.

- Medication dates including study medications, concomitant medications, and antineoplastic therapies administered after study treatment discontinuation.
- Adverse event dates.
- Last contact date collected on the 'Survival information' eCRF (only if the patient status is not unknown).
- Randomization date.
- The cut-off date will not be used for last contact date, unless an actual assessment or patient contact was performed.

Important note: imputed dates (e.g. the analysis cut-off date programmatically imputed to replace the missing end date of a dose administration record) will not be used to derive the last contact date.

The last contact date will be used for censoring of patients in the analysis of overall survival.

#### **2.1.2.8 Scheduled study visit and window for the analysis**

In order to summarize longitudinal data per time point, assessments will be allocated to visits using predefined time windows. Unless otherwise specified, when more than one assessment is available for a visit, all assessments will be listed under the visit while only the assessment closest to the planned day for the visit will be used for summaries and analyses.

Time windows are provided in [Table 2-1](#). Time windows for measurements to be described by visit.

**Table 2-1 Time windows**

Assessment	Visit	Time Window
Efficacy Assessments		
Tumor response for imaging assessments	Screening	Baseline
	C3D1	Week 8 ± 3 days every 8 weeks (2 cycles) during the first 12 month, i.e. C5D1 ± 3 days, C7D1 ± 3 days, C9D1 ± 3 days, C11D1 ± 3 days, C13D1 ± 3 days
	C16D1	Week 60 ± 3 days every 12 weeks (3 cycles) ... i.e. C19D1 ± 3 days, C22D1 ± 3 days, C25D1 ± 3 days ...
	EOT	EOT - 28 days

Notes:

C = cycle, D = Day

All other assessments (i.e. laboratory evaluations etc.) the reported visit will be used

### 2.1.2.9 Imputation rule of partial or missing dates/data

#### Imputation rule of partial or missing dates

The following rule will be applied to handle partial dates. When the day is missing, it is imputed to the 15th of the month (e.g., DEC2007 imputed to 15DEC2007). When the day and month are both missing then the date is imputed to July 1st of that year (e.g., 2007 imputed to 01JUL2007). All imputed data are flagged in the listings.

Standard imputation rules for adverse events (AEs) and concomitant medications partial or missing dates will be used.

For computation of time intervals (e.g. elapse time between initial diagnosis to first recurrence/relapse), time interval should be set to missing when the imputation rule leads to a negative value.

As of the date of data cutoff for the purposes of reporting, continuing events (e.g. adverse events, concomitant medication, etc.) will be summarized using the cut-off date as the date of completion, with an indication within listings that the event is continuing.

For patients who discontinue the study with ongoing events, the discontinuation date will be used as the completion date of the event with the appropriate censoring.

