Enrollment to this study was halted on 20-Nov-2015. Based on the small number of patients enrolled prior to the enrollment halt, the primary endpoint will not be obtained and therefore it is no longer necessary for patients to continue to receive placebo. With this in mind, ongoing patients will be unblinded in order to permit crossover to LEE011 for those patients receiving placebo.

Other changes implemented in this amendment:

[figure not shown]
- To update the preclinical safety pharmacology and toxicology sections to include recent data on teratogenicity of LEE011.
- To correct minor typographical and grammatical errors throughout the document.

Study status:

The CLEE011X2201 study started enrollment on 26-February-2015. Enrollment to this study was halted on 20-Nov-2015. Prior to recruitment halt, a total of 10 patients were enrolled. As of 18-Aug-2017, there are 4 patients on treatment, 3 of which are blinded and 1 has crossed over to LEE011 treatment.

Changes to the protocol

- Section 1.2.1.3 – updated preclinical safety pharmacology and toxicology
- Section 4.1 – revised treatment procedures after early study termination
- Section 4.1.2 – added language to facilitate unblinding of ongoing patients and allow placebo patients to crossover to LEE011 treatment if the investigator believes it is in the best clinical interest of the patient
- Section 4.1.3, 4.1.4 and 4.1.5 – revised follow-up procedures after early study termination
- Section 4.1.6 – revised crossover treatment procedures after study termination and following patient enrollment to a LEE011 rollover clinical trial (CLEE011X2X01B)
- Section 4.3 – added language to permit patient rollover to CLEE011X2X01B
- Section 4.3 – revised to align with Section 10.4 regarding when a primary CSR will be produced
- Section 7.1.3 – added transfer to a LEE011 rollover clinical trial (CLEE011X2X01B) as a reason for end of treatment
- Section 7.1.3 – changed parent/guardian decision to patient/parent/guardian decision

- Section 7.1.5.1 – revised follow-up procedures following patient enrollment to a LEE011 rollover clinical trial (CLEE011X2X01B)
- Section 7.1.5.2 and 7.1.5.3 – revised follow-up procedures after early study termination
- Section 10 – revised to clarify CSR reporting after early study termination or patient enrollment to a LEE011 rollover clinical trial (CLEE011X2X01B)

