14.1.35 Incomplete assessment dates

[figure not shown]
All investigation dates (e.g. X-ray, CT scan) must be completed with day, month and year.

If one or more investigation dates are incomplete but other investigation dates are available, this/these incomplete date(s) are not considered for calculation of the assessment date (and assessment date is calculated as outlined in [Section 14.1.25](#)). If all measurement dates have no day recorded, the 1st of the month is used.

If the month is not completed, for any of the investigations, the respective assessment will be considered to be at the date which is exactly between previous and following assessment. If a previous and following assessment is not available, this assessment will not be used for any calculation.

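### SAP 2.1.2.9 imputes partial death dates with no lower bound, so a death can be dated before first dose, first crossover dose or last visit; only the death outputs are affected

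*SAP*

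**What the plan says.** SAP 2.1.2.9 gives one general rule for partial dates: "When the day is missing, it is imputed to the 15th of the month", and "When the day and month are both missing then the date is imputed to July 1st of that year". Two kinds of date are taken out of it: "Standard imputation rules for adverse events (AEs) and concomitant medications partial or missing dates will be used". Nothing ties an imputed date to randomization, first dose, last visit or last contact. For computed intervals, the "time interval should be set to missing when the imputation rule leads to a negative value".

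Protocol 14.1.36 also uses the 15th for a death or last-contact date that lacks a day, again without a floor. It has no rule for a missing month, so 1 July comes from the SAP alone.

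Protocol 14.1.35 treats scan dates differently. "If all measurement dates have no day recorded, the 1st of the month is used"; with the month missing, the assessment is placed "at the date which is exactly between previous and following assessment", or not used if those neighbours do not exist.

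Among the outputs the SAP keeps, section 3.6.2 summarizes and lists deaths, and "on treatment deaths will be flagged". Sections 3.4.2, 3.5 and 4 withdraw the PFS, OS and response analyses.

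**The concern.** A death cannot precede the last day the patient was dosed or seen. A rule that ignores those days can return an impossible date, and three retained derivations read that date:

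- the on-treatment flag, whose window runs from first dose to last dose plus 30 days (SAP 2.1.2.6);
- the study day shown in listings, which for deaths counts from randomization (SAP 2.1.2.4);
- the split between placebo and crossover LEE011, made at the first LEE011 dose (SAP 2.1.2.6 and 3.6).

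SAP 2.1.2.6 also restricts selected death summaries to on-treatment events, and SAP 3 confines summary tables to the two randomized groups. A wrong flag or attribution can therefore move a death out of one summary or into another.

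**Working it through.** The patient dates below are illustrations, not trial data.

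**Inputs.** Imputation rules: SAP 2.1.2.9. Study day = event date − randomization date + 1: SAP 2.1.2.4. Enrolment: "The CLEE011X2201 study started enrollment on 26-February-2015" (Protocol, Amendment 3, study status); the same place gives the halt on 20-Nov-2015 and 10 patients.

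**The plan's own example.** Randomized 15 Dec 2013, died 28 Dec 2013: 28 − 15 + 1 = 14, as SAP 2.1.2.4 states.

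**1. Only the year known.** Randomized and first dosed 10 Sep 2015, last dose 20 Nov, last visit 25 Nov, death recorded as 2015.
- Imputed date 1 Jul 2015, which is 71 days before randomization. Study day = −71 + 1 = −70.
- 1 July precedes first dose, so the death is flagged not on-treatment.
- The death must lie between 25 Nov and 31 Dec: 6 + 31 = 37 possible days. The window closes on 20 Nov + 30 = 20 Dec, so 6 + 20 = 26 of the 37 days are on-treatment. None of the 37 is before first dose.

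**2. Month known, in the month of first dose.** Randomized and first dosed 20 Mar 2015, death recorded as March 2015.
- Imputed date 15 March. Study day = 15 − 20 + 1 = −4, flagged not on-treatment.
- The true date is 20 to 31 March, at most 11 days after first dose and so inside last dose + 30. The flag is certainly wrong.

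**3. Month known, in the month of crossover.** First LEE011 dose 20 March, death recorded as March.
- Imputed date 15 March, before the first LEE011 dose, so the death goes to placebo. It can only have occurred on or after 20 March.

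**4. Before the last visit.** Last visit 25 March, death on 28 March recorded as March.
- Imputed date 15 March, 10 days before the visit. The interval from an earlier randomization stays positive, so nothing in the SAP catches it.

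**5. Share of calendar dates exposed.** This assumes first dose on the day of randomization and dates spread evenly from 26 Feb to 20 Nov 2015.
- Window: 3 + 245 + 20 = 268 days (February, March to October, November).
- Death known only as 2015: first dose falls after 1 July on 30 + 31 + 30 + 31 + 20 = 142 days; 142/268 = 53%. The study day is negative for 141 of these and zero for one (2 July).
- Death in the month of first dose, day missing: first dose falls after the 15th on 133 days; 133/268 = 50%. The study day is negative for 124 and zero for 9.
- Last visit and death in the same 30-day month, day missing: if all pairs with death on or after the visit are equally likely, the 15th precedes the visit in 120 of 465 pairs (26%). If instead the visit day alone is uniform, it is 15 of 30 (50%).

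These shares apply per affected record. The documents do not say how many death dates are partial.

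**6. Scan dates, for comparison.** With every measurement date lacking a day, the SAP gives the 15th and the protocol the 1st: 14 days apart. With only the year known and neighbouring scans on 12 Oct 2015 and 1 Feb 2016, the protocol midpoint is 7 Dec 2015 and the SAP date 1 Jul 2015: 159 days apart. SAP 4 withdraws every PFS and response output that would use these dates.

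**The case against.** The strongest case against is that this is housekeeping. The main death summary is by treatment, system organ class and preferred term and uses no interval, so no death disappears from it. The protocol asks for complete dates (14.1.35, 14.1.36), queries missing values (9.4) and contacts patients for survival every 12 weeks (7.1.5.3), so partial death dates should be rare. Imputed values are flagged in listings, and with 10 patients an impossible date would be noticed. All of that stands and keeps the point small. It does not remove it, because a listing mark does not correct an on-treatment flag or a treatment attribution already derived from the date.

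A reader might infer more than the documents support:

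- *That early events lose their times and bias PFS or OS.* The set-to-missing rule could do this in principle, but those analyses are withdrawn.
- *That the scan-date conflict shifts progression by 14 days in every case.* It reaches no planned output, and the 14 days arise only when every measurement date at an assessment lacks a day; otherwise Protocol 14.1.35 ignores the partial one. SAP 3.4.1 also points to Appendix 1 for PFS.
- *That the SAP departs from the protocol on deaths.* For a missing day they agree; only 1 July is new.
- *That the rule contradicts the last contact date in SAP 2.1.2.7.* That date is derived only for patients not known to be dead.
- *That any imputed date before the last dose changes the flag.* With last dose 20 Nov, last visit 25 Nov and death in November, both the imputed 15 Nov and the possible 25 to 30 Nov fall inside the window, provided first dose was on or before 15 Nov.

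**Conclusion.** The point holds as a minor defect in a stated rule. Followed literally, SAP 2.1.2.9 can date a death before first dose, before the first crossover LEE011 dose or before the last visit. In the first two cases it can change the on-treatment flag, the displayed study day or the group to which the death is assigned. About half of the possible first-dose dates are exposed for a death known only as 2015 (53%) or only by the month of first dose (50%), on the even-spread assumption. The expected number of affected deaths cannot be stated, because the frequency of partial dates is not given; among 10 patients it may be none. The conclusion rests on the SAP text as written and on the short close-out reporting in SAP 4. No efficacy conclusion is at risk.

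**What to change.** Add to SAP 2.1.2.9 that a partial death date is set to the later of the imputed date and the patient's last complete date known alive, taken from visits, doses, assessments and contacts. Derive that known-alive date for patients who died as well, since SAP 2.1.2.7 does not. Keep the result within the reported month or year; if the known-alive date falls after it, the record is a data conflict to query. Because the floor can land on the day of the first crossover dose, also say which group that day belongs to: SAP 2.1.2.6 and 3.6 speak only of events before and after it.

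For consistency, refer partial tumor-assessment dates to Protocol 14.1.35, and limit the set-to-missing rule to historical intervals such as diagnosis to relapse.

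The cost is a few sentences and minor programming. No new data are needed, and no sample size, alpha or power figure changes.
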